6.5.7.6.2 Sensitivity Analyses for Secondary Efficacy Endpoints

For quantitative secondary efficacy endpoints, two-sample t-tests, Wilcoxon rank sum tests and mixed-effect repeated measures analysis comparing treatment groups will be performed as sensitivity analyses.

The mixed-effect repeated measures model will include treatment, baseline value, visit, and the interaction between treatment and visit as fixed effects, and subject as a random effect. An unstructured covariance matrix will initially be used to model the covariance among repeated measures; however, if the model fails to converge using this covariance structure, either heterogeneous TOEPLITZ, homogeneous TOEPLITZ, or compound symmetry will be implemented according to the AICc.

6.5.7.6.3 Sensitivity Analyses for Other Pre-specified Efficacy Endpoints

For quantitative efficacy variables, two-sample t-tests, Wilcoxon rank sum tests and mixed-effect repeated measures analysis will be presented as sensitivity analyses.

For qualitative efficacy variables, Pearson chi-squared analysis comparing the treatment groups will be performed as sensitivity analyses.

Sample Pearson chi-squared analysis code:

PROC FREQ DATA=INDATA;
 TABLES <TREATMENT>*<ENDPOINT> / CHISQ;
RUN;

6.5.8 Statistical/Analytical Issues

6.5.8.1 Study Days

Study Day 1 will be defined as the date of Visit 1/Day 1. For events before the Day 1 visit, the study day will be calculated as the difference in day between the Day 1 visit and the date of interest. Thus, the day prior to the Day 1 visit will be defined as Day -1.

6.5.8.2 Analysis Visits

The eCRF nominal study visits will be used for analysis. For subjects who withdraw from the study, if they withdraw at a regular scheduled visit, the data collected at the time of withdrawal will be summarized under the regular visit; if they withdraw between scheduled visits, the early termination visit will be treated as an unscheduled visit. For the purposes of table summarization, the first visit for each nominal study visit will be used.

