Subjects who terminate early during the treatment period will be asked to complete all assessments as indicated at Visit 4 on the schedule of assessments prior to commencement of any alternative dry eye therapy (if considered possible). Subjects who are terminated early from the trial will not be replaced.

Trial Flow

All subjects will be expected to progress from screening through trial exit. All subjects will follow the trial structure as shown in [Figure 1](#).

[figure not shown]

Figure 1 Study 904 Flow Chart

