6.5.8.6 Handling of Dropouts or Missing Data

Missing data will be handled as follows. Missing data for other data points not covered below will be left as missing. Nominal visits for subjects who withdraw will be handled per Section 6.5.8.2.

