6.5.8.6.1 Imputation Method for Efficacy Endpoints

The primary analysis will be completed on the FAS with available data per subject, assuming the overall study discontinuation rate is \leq 5%. If the overall study discontinuation rate is \geq 5% then the primary analysis will be based on the primary imputation methodology as defined Section 6.5.7.3 and the available data analyses will become robustness analyses.

Additionally, robustness analyses will include repeating the primary analysis on the per protocol set (PPS); the FAS imputing missing data using last observation carried forward (LOCF); the FAS imputing missing data using Markov Chain Monte Carlo (MCMC) multiple imputation methodology under different assumptions of missingness (at random and not at random) each using 30 imputed values.

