6.5.9.4.3 Dilated Fundoscopy Examination

A dilated fundoscopy examination will be performed during the trial at screening, Visit 4 and early termination. Observations will be graded as Normal, Abnormal CS or Abnormal NCS. Vitreous, retina, macula, choroid and optic nerve will be examined. If 'Check if no changes since Visit 0' is checked, the results of the tests at Visit 0 will be used for analysis at that timepoint. Listings will display 'No changes since Visit 0'. Descriptive statistics for the grading by each domain will be presented for study eye and fellow eye by treatment and overall at baseline and all post-baseline visits in the SAF. Shifts from baseline indicative of worsening will also be summarized. Worsening is defined as a shift from normal to abnormal

not clinically significant, normal to abnormal clinically significant, and abnormal not clinically significant to abnormal clinically significant.

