6.5.9.4.4 Intraocular Pressure

Intraocular pressure (IOP) will be measured in each eye by contact tonometry by the examiner and the results will be recorded in mmHg at screening, Visit 4 and early termination. A single measurement will be made to obtain a determination of IOP. Descriptive statistics for the IOP measurement will be presented for study eye and fellow eye by treatment and overall at baseline and all post-baseline visits in the SAF. Changes from baseline will also be summarized.

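### Read literally, the SAP's visit rule leaves early-termination IOP and fundoscopy results from between-visit withdrawals out of the by-visit safety tables, and it does not say whether LOCF may use early-termination values

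*SAP*

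**What the plan says.** **Collection.** Protocol 4.3 states: "Subjects who terminate early during the treatment period will be asked to complete all assessments as indicated at Visit 4". Protocol 8.4.2 repeats the request, and the schedule of assessments puts ET in the same column as Visit 4. For IOP, SAP 6.5.9.4.4 says "the results will be recorded in mmHg at screening, Visit 4 and early termination". For the fundus, SAP 6.5.9.4.3 says "A dilated fundoscopy examination will be performed during the trial at screening, Visit 4 and early termination". Neither examination is scheduled at Visits 1, 2 or 3.

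**Assignment to visits.** SAP 6.5.8.2 contains these linked rules:

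- "The eCRF nominal study visits will be used for analysis".
- Exit data collected at a regular visit are summarized under that visit.
- For other withdrawals, "if they withdraw between scheduled visits, the early termination visit will be treated as an unscheduled visit".
- In tables, only the first record of each nominal visit counts.

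The missing-data section points back to these rules: "Nominal visits for subjects who withdraw will be handled per Section 6.5.8.2" (SAP 6.5.8.6).

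**Use.** SAP 6.5.9.4 summarizes visual acuity, slit-lamp findings, fundoscopy and IOP by visit. The table index titles the IOP and fundoscopy results tables by visit, but not the worsening-shift tables. No section gives ET a row. LOCF on the FAS is a robustness analysis for the primary endpoints (SAP 6.5.7.3 and 6.5.8.6.1), and neither place defines which records may be carried forward.

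**The concern.** The protocol goes to some trouble to obtain a full exit examination, and SAP 6.5.9.4 names ET as a collection point. The visit rule then detaches that examination from every nominal visit unless the withdrawal happens to coincide with a scheduled one. Whether exit data are tabulated would depend on the day the subject left.

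For visual acuity and slit-lamp findings the loss is partial, because Visits 2 and 3 also provide values. For IOP and fundoscopy nothing else is scheduled after screening. Safety is compared only descriptively, so the tables are the comparison, and withdrawals for adverse events are among the subjects who could be missing from them.

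The LOCF question is separate. If unscheduled values are not eligible, the value carried forward is an older scheduled one. A subject who leaves before Visit 2 has only baseline, and the SAP does not say whether that counts as zero change or as missing. Two programmers could produce different LOCF results from the same text.

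**Working it through.** **1. The plan's own figures** (Protocol 10.3, SAP 6.5.10)

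- Inflation for discontinuation: 250 / (1 − 0.10) = 277.8, so 278 per arm; the plan uses 280. Expected completers: 280 × 0.90 = 252 per arm.
- Power for tCFS: 1.0 / (2.8 × √(2/250)) = 3.99, and Φ(3.99 − 1.96) = 97.9%. Dryness Score has the same ratio (10/28), so also 97.9%. Joint power under independence: 0.979 × 0.979 = 95.8%.

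All of these reproduce and none is in dispute. Only the 10% discontinuation rate is used below.

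**2. Tracing one subject** who leaves between Visits 3 and 4 and attends an ET visit

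| Step | Rule | Result |
|---|---|---|
| Examination | Protocol 4.3, 8.4.2 | Visit 4 assessments, including IOP and fundoscopy |
| Visit label | SAP 6.5.8.2 | Unscheduled |
| By-visit IOP and fundoscopy tables | SAP 6.5.8.2, 6.5.9.4, table index | No Visit 4 record, and no ET row: not tabulated |
| Worsening-shift tables | Table index | Uncertain: not titled by visit, but the first-record rule covers tables generally |
| Listings | Table index | Present (IOP, fundoscopy, unscheduled visits) |
| LOCF for Day 57 | SAP 6.5.7.3, 6.5.8.6.1 | Undefined: the ET value, or Visit 3 on a nominal-visit reading |
| Primary analysis | SAP 6.5.7.3 | Unchanged: available Day 57 data, or BOCF and multiple imputation at 5% or more discontinuation |

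**3. How many subjects**

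Number affected = 560 × discontinuation rate × share leaving between visits with an ET examination. The documents do not give that share, so 25% to 100% is an assumption. The second row is the largest count below the 5% threshold: 27/560 = 4.8%.

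| Withdrawals | 25% | 50% | 75% | 100% |
|---|---|---|---|---|
| 560 × 0.10 = 56 | 14 | 28 | 42 | 56 |
| 27 | about 7 | about 14 | about 20 | 27 |

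**4. Effect on the safety tables**

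In the extreme case the by-visit tables hold 252 instead of 280 per arm. For a finding seen in no subject, the exact one-sided 95% upper bound is 1 − 0.05^(1/n): 1.06% at n = 280 and 1.18% at n = 252. The loss of precision is small; what matters is which subjects are missing.

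**5. Effect on LOCF**

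Shift in an arm mean = share of the arm affected × mean gap between the ET value and the value used instead. With 14/560 = 2.5% to 56/560 = 10% affected:

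- tCFS: 0.025 to 0.10 points per 1-point gap.
- Dryness Score: 0.25 to 1.0 points per 10-point gap.

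The treatment difference moves only by the difference between the two arms' shifts.

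**The case against.** The strongest reply is that the SAP never says these values are excluded.

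- **LOCF.** Calling a visit unscheduled does not bar its values from being carried forward. SAP 6.5.8.3 counts any measurement after the first dose as post-baseline, and the first-record sentence is confined to tables. This stands: a reader might infer that the last value is lost to LOCF, but the documents leave its eligibility undefined.
- **Safety tables.** SAP 6.5.9.4 names ET as a timepoint and promises summaries at every post-baseline visit, and the eCRF that defines the nominal visits is not among the documents. This softens the point without removing it. SAP 6.5.8.2 expressly relabels the between-visit ET, and nothing gives the unscheduled record a row. For the shift tables the reply has more force, so exclusion there is only possible.
- **Other sources.** ET results stay in listings, adverse-event tables do not depend on visits, and Protocol 8.4.3 permits IOP and fundoscopy at other unscheduled visits. All true. The ET result is therefore the only scheduled post-baseline value, and only for these two examinations.
- **Keeping ET out of Day 57 is sensible.** Agreed; the fix preserves it.
- **Count.** Lost-to-follow-up subjects have no separate ET visit (Protocol 4.2), the ET examination is done only where possible (Protocol 4.3), and subjects who stop treatment are encouraged to keep attending (Protocol 8.4.2). So 56 is a ceiling, and the true minimum is unknown.

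**Conclusion.** The point holds for the ocular safety tables on a literal reading of SAP 6.5.8.2, and as an unspecified rule for LOCF. The ceiling is 56 of 560 subjects. It requires that the planned 10% discontinuation occurs, that every withdrawal falls between visits, and that every such subject attends an ET examination.

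Two stronger conclusions are tempting and should not be drawn:

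- **That the safety tables are biased towards completers in a known direction.** The documents do not say who leaves between visits or why, and show no direction for any effect on the treatment comparison. Selective loss of subjects who withdrew for adverse events is a risk, not a demonstrated bias.
- **That the efficacy conclusion is at stake.** LOCF is one of several robustness analyses, and the primary analysis does not use it at any discontinuation rate.

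This is a cheap improvement worth making before unmasking, not a threat to the trial's main result.

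**What to change.** Amend SAP 6.5.8.2 and 6.5.9.4:

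1. Add a row for the last post-baseline value (Visit 4 or ET) to the IOP and fundoscopy tables, and likewise for visual acuity and slit-lamp biomicroscopy.
2. Include ET results in the worsening-shift tables.
3. State that ET efficacy values are not assigned to Day 57 but count as the last observation for LOCF.

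The cost is SAP wording, one extra analysis-visit flag and one table row, with no new data collection. The drawback is that the new row mixes exposure durations. It should therefore be labelled as such and shown beside the Visit 4 row, not in place of it.

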6.5.8.3 Study Baseline

Baseline measures are defined as the last non-missing measure prior to the initiation of randomized study treatment as documented in the subject dosing diary. Per the schedule of assessments in the protocol, this is expected to be the Visit 1 value. Measurements that are obtained after the first dose of randomized study treatment will be considered post-baseline values. If a measurement of a variable is not made on a given subject prior to the first dose of randomized study treatment, then that subject will be considered not to have a baseline value for that variable. CFB is defined as post-baseline assessment minus baseline assessment.

6.5.8.4 CDISC Standards

The exchange and terminology standards outlined in Section 4 will be used to create SDTM domains and ADaM datasets. A reviewer's guide and define.xml will be produced for each set. The ADaM datasets will be used to support all tables, listings, and figures with the exception of the pregnancy results listing which will be generated from SDTM. All data in the ADaM datasets will be used as the population for listings. At least one listing will be created for each ADaM dataset to display (a) most collected variables, and (b) derived variables used in the tables and figures. The source listing(s) will be referenced in all

table and figure footnotes.

6.5.8.5 Adjustment for Covariates

The primary endpoints are CFB in total corneal fluorescein staining (NEI scale) at Day 57 and CFB of Dryness Score (VAS) at Day 57. The two primary endpoints will be analyzed separately using an ANCOVA model with baseline measurement as a numeric covariate and treatment as the main effect.

Subject randomization is stratified by clinical site and dryness score $<70 \text{ vs} \ge 70 \text{ (VAS)}$ at baseline (Visit 1). The analyses will not be adjusted for the stratification factors.

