4.5 Justification of Trial Design

This trial is designed as a confirmatory trial to the previously conducted phase 2 trial NVU-002 and a supportive trial to the ongoing phase 3 trial NVU-003 in subjects with DED associated with MGD. This population is considered to respond best based on the mode of action and clinical data.

The trial will be a randomized, double-masked, saline controlled trial to demonstrate efficacy and safety of NOV03 after a 2-month treatment duration. Vehicle controlled trials are currently the standard for DED trials, however, as NOV03 is a 100% single component product, saline solution has been selected as comparator given that this most likely best reflects a placebo treatment. Randomization and double masking are state of the art measures to reduce bias. Fast onset of efficacy is important for subjects and their compliance to therapies, thus early demonstration of efficacy (e.g. at 2 month) is desired and highly clinically relevant. Moreover, DED is a fluctuating condition with recurring dry eye complaints that may be linked to seasonal and/ or environmental changes ([Van Setten et al., 2016](#)), thus a primary endpoint assessment following a shorter treatment duration is considered clinically relevant and has a greater potential to capture the true drug effect.

The two primary endpoints, tCFS and Dryness Score, will be tested in a hierarchical order with total corneal fluorescein staining being tested first as the NVU-002 data for this endpoint is stronger. The hierarchical testing has been selected to protect the α – error.

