5.3 Inclusion Criteria

Subjects will be eligible to participate in this trial if they **meet all** following criteria:

1. Be at least 18 years of age at the time of consent.
2. Provide written informed consent.
3. Have a subject reported history of Dry Eye Disease in both eyes for at least 6 months prior to Visit 0.
4. Have Tear film break-up time (TFBUT) ≤ 5 sec at Visit 0 and Visit 1.
5. Have Ocular Surface Disease Index (OSDI[®]) ≥ 25 at Visit 0 and Visit 1.
6. Have an unanesthetized Schirmer's Test I ≥ 5 mm at Visit 0 and Visit 1.
7. Have Meibomian Gland Dysfunction (MGD) defined as total MGD score ≥ 3 (secretion of 5 central glands on lower eyelid will be evaluated, each will be scored

from 0-3; 0 = normal, 1 = thick/yellow, whitish, particulate 2 = paste; 3 = none/occluded; total score will range from 0-15) at Visit 0 and Visit 1.

8. Have a total corneal fluorescein staining score of $4 \leq X \leq 11$ (i.e. sum of inferior, superior, central, nasal, and temporal) according to the National Eye Institute (NEI) scale at Visit 0 and Visit 1.
9. Have at least one eye (the same eye) satisfy all criteria for 4, 6, 7, and 8 above at Visit 0 and Visit 1.
10. Be able and willing to follow instructions, including participation in all trial assessments and visits.

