10.4.2 Unit of Analysis

For efficacy endpoints, the unit of analysis will be the study eye as defined by the following:
Study Eye: Eyes are eligible for analysis if they meet all of the inclusion criteria. In the case that both eyes are eligible for analysis, the worst eye shall be chosen, and this will be defined as the eye with worse (higher) total corneal staining at Visit 1. If the total corneal staining is the same in both eyes then the right eye will be selected as the study eye.

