6.1.2 Trial Procedures

The schedule of assessments, as outlined in the trial protocol, is presented below in Table 1.

Table 1. Schedule of Assessments

Procedure	Visit 0 Within 14 days before Visit 1 (Day -14 to -1)	Visit 1 Day 1	Visit 2 Day 15 ± 1	Visit 3 Day 29 ± 2	Visit 4 /(ET) Day 57 ± 2
Informed Consent / HIPAA	\mathbf{X}				
Demographics	X				
Medical/Surgical History	X	X			
Previous/Concomitant Medication	X	X	X	X	X
Inclusion/Exclusion Criteria	\mathbf{X}	X			
Urine Pregnancy Test	X	X			X
Eyedrop Acceptability Questionnaire					X
Dryness Score (VAS severity of dryness)*		X	X	X	X
VAS*		X	X	X	X
OSDI*	X	X	X	X	X
Eyedrop Acceptability Questionnaire*					X
Visual Acuity (ETDRS)	X	X	X	\mathbf{X}	X
Slit-Lamp Biomicroscopy	X	X	X	X	X
TFBUT*	X	X			X
Corneal Fluorescein Staining (NEI scale)*	X	X	X	X	X
Meibomian Gland Assessment (MGD score)*	X	X			X
Schirmer's Test I (without anesthesia)*	X	X			X
Intraocular Pressure	X				X
Dilated Fundoscopy	X				X
Randomization (via IRS)		X			
In-office instillation of randomized IMP		X			
Instillation Comfort Questionnaire		X			
Adverse Event Query	X	X	X	X	X
Dosing Diary Dispensation and/or Review		X	X	X	X
Dispensation of trial medication		X	X	X	

Protocol Number: 904

Procedure	Visit 0 Within 14 days before Visit 1 (Day -14 to -1)	Visit 1 Day 1	Visit 2 Day 15 ± 1	Visit 3 Day 29 ± 2	Visit 4 /(ET) Day 57 ± 2
Collection of trial medication			X	X	X
Trial Exit					X

^{*=}Assessment to be conducted in the order as depicted in the Schedule of Assessments; ETDRS = Early Treatment of Diabetic Retinopathy Study; HIPAA = Health Information Portability and Accountability Act; NEI = National Eye Institute; OSDI = Ocular Surface Disease Index; TFBUT = Tear Film Break Up Time;

ET = Early Termination; VAS: burning/stinging, sticky feeling, foreign body sensation, itching, blurred vision, sensitivity to light, pain, frequency of dryness, and awareness of dry eye symptoms

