6.2.1 Inclusion Criteria

Subjects will be eligible to participate in this trial if they **meet all** following criteria:

- 1. Be at least 18 years of age at the time of consent.
- 2. Provide written informed consent.
- 3. Have a subject reported history of Dry Eye Disease in both eyes for at least 6 months prior to Visit 0.
- 4. Have Tear film break-up time (TFBUT) ≤5 sec at Visit 0 and Visit 1.
- 5. Have Ocular Surface Disease Index (OSDI[®]) ≥25 at Visit 0 and Visit 1.
- 6. Have an unanesthetized Schirmer's Test I \geq 5 mm at Visit 0 and Visit 1.
- 7. Have Meibomian Gland Dysfunction (MGD) defined as total MGD score ≥ 3 (secretion of 5 central glands on lower eyelid will be evaluated, each will be scored from 0-3; 0 = normal, 1 = thick/yellow, whitish, particulate 2 = paste; 3 = none/occluded; total score will range from 0-15) at Visit 0 and Visit 1.
- 8. Have a total corneal fluorescein staining score of $4 \le X \le 11$ (i.e. sum of inferior, superior, central, nasal, and temporal) according to the National Eye Institute (NEI) scale at Visit 0 and Visit 1.
- 9. Have at least one eye (the same eye) satisfy all criteria for 4, 6, 7, and 8 above at Visit 0 and Visit 1.
- 10. Be able and willing to follow instructions, including participation in all trial assessments and visits.

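### The corneal staining ANCOVAs adjust only for the Visit 1 score; adding the Visit 0 score, which is already collected, would cost little and may tighten the estimates slightly

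*SAP*

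**What the plan says.** - **Two readings before treatment.** The schedules of assessments (Protocol Appendix 1, SAP 6.1.2) mark staining at Visit 0 and at Visit 1. Protocol 5.3, criterion 8, requires a total score of 4 to 11 "according to the National Eye Institute (NEI) scale at Visit 0 and Visit 1". Criterion 9, repeated in SAP 6.2.1, ties this to one eye: "Have at least one eye (the same eye) satisfy all criteria for 4, 6, 7, and 8 above at Visit 0 and Visit 1". A correctly enrolled subject therefore has a Visit 0 score for the study eye.
- **One reading is the baseline.** SAP 6.5.8.3 states: "Baseline measures are defined as the last non-missing measure prior to the initiation of randomized study treatment". It adds that "this is expected to be the Visit 1 value".
- **One baseline term in the model.** SAP 6.5.8.5 specifies "an ANCOVA model with baseline measurement as a numeric covariate and treatment as the main effect". The sample code in SAP 6.5.7.3 has treatment and a single baseline term, and Protocol 10.4.5 describes the same model. The imputation code (Protocol 10.4.3, SAP 6.5.7.3) and the repeated-measures model (SAP 6.5.7.6.1) also carry one baseline variable.
- **Study eye.** When both eyes qualify, Protocol 10.4.2 takes "the eye with worse (higher) total corneal staining at Visit 1".
- **Dryness Score.** It is not taken at Visit 0, so the point concerns staining only.

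**The concern.** If a staining score is the eye's usual level plus short-term variation and grading error, one reading measures that level imperfectly, and a second reading taken before treatment should predict Day 57 beyond the first. The worse-eye rule adds to this. When both eyes qualify, the Visit 1 score is both the covariate and the quantity on which the eye was chosen, so it is partly selected on its own error; Visit 0 plays no part in that choice.

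At stake is the width of the confidence intervals for tCFS at Day 57 (the first primary endpoint), tCFS at Day 15 and cCFS at Day 57 (both gated secondaries). The tCFS Day 57 test opens the whole hierarchy: if it fails, neither the Dryness Score nor any secondary endpoint can be claimed.

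**Working it through.** **Inputs from the documents.** tCFS difference -1.0, SD 2.8, two-sided alpha 0.05, 250 evaluable per arm, stated power 97.9% (Protocol 10.3, SAP 6.5.10). The Protocol synopsis takes its planning values from a phase 2 (NVU-002) ANCOVA that already had baseline as a covariate, so I treat 2.8 as the SD after adjustment for one baseline.

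**Step 1: reproduce the plan's figure.** The standard error is 2.8 × √(2/250) = 0.250. Power is Φ(1.0/0.2504 − 1.96) = Φ(2.033) = 97.9%. The stated figure is right for the planned model.

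**Step 2: effect of a second covariate.** Let a be the Visit 0–Visit 1 correlation, b Visit 0–Day 57 and c Visit 1–Day 57. With both readings in the model,

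R² = (b² + c² − 2abc)/(1 − a²), and the residual variance ratio is (1 − R²)/(1 − c²).

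The new SD is 2.8 × √ratio. The documents give none of these correlations, so all values below are assumptions.

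| a / b / c | Variance ratio | SD | tCFS power |
|---|---|---|---|
| 0.3 / 0.3 / 0.3 | 0.947 | 2.72 | 98.4% |
| 0.5 / 0.5 / 0.5 | 0.889 | 2.64 | 98.9% |
| 0.7 / 0.7 / 0.7 | 0.830 | 2.55 | 99.2% |
| 0.6 / 0.45 / 0.5 | 0.953 | 2.73 | 98.3% |
| 0.5 / 0.3 / 0.4 | 0.984 | 2.78 | 98.1% |
| 0.7 / 0.4 / 0.5 | 0.994 | 2.79 | 98.0% |
| 0.6 / 0.3 / 0.5 | 1.000 | 2.80 | 97.9% |

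In the last row R² = (0.09 + 0.25 − 0.18)/0.64 = 0.25, which equals c². Visit 0 then adds nothing.

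**Step 3: allow for the entry window.** Restricting both visits to 4–11 narrows the range of the covariates and weakens them as predictors. A simulation drew integer scores from a normal distribution with mean 7 and SD 3 (both assumed), with equal underlying correlations of 0.3, 0.5 and 0.7, and kept only subjects within 4–11 at both visits. It gave ratios of 0.974, 0.938 and 0.884, a reduction of about 3% to 12%. Simulations that also applied the worse-eye rule gave 1–5% under one set of assumptions and about 2–13% under another. With the zero-gain case included, the working range is about 0% to 13%.

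**Step 4: translate to power and precision.** At a ratio of 0.87 the SE is 0.2504 × √0.87 = 0.2336, and power is Φ(1.0/0.2336 − 1.96) = 99.0%. The 95% confidence half-width falls from 1.96 × 0.2504 = 0.491 to 1.96 × 0.2336 = 0.458 staining points.

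**Step 5: a smaller true effect.** At a difference of -0.7, planned power is Φ(0.7/0.2504 − 1.96) = 79.8%. At ratios of 0.974 and 0.884 it becomes Φ(0.7/0.2472 − 1.96) = 80.8% and Φ(0.7/0.2355 − 1.96) = 84.4%.

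**The case against.** - **There is no error to correct.** ANCOVA on the last value before dosing is valid, is stated consistently in both documents, and is the form of model behind the phase 2 planning estimates. This stands: the point is an optional improvement.
- **The gain is unknown and may be nil.** Visit 0 is further from Day 57 than Visit 1 and may be the weaker predictor. This stands. A reader might infer a variance reduction as large as 18%, which the formula gives at 0.3/0.5/0.5. That requires Visit 0 to correlate better with Day 57 (0.5), across the treatment period, than with Visit 1 (0.3), at most 14 days later and still untreated. Nothing in the documents supports that pattern.
- **The plan already has a margin.** It uses -1.0 (SD 2.8), where phase 2 gave -1.2 (2.5). At the phase 2 values, 250 per arm has over 99.9% power. This stands, and it limits the benefit unless the effect is smaller than planned.
- **The protocol's remark on fluctuation is weak support.** Protocol 4.5 says "DED is a fluctuating condition with recurring dry eye complaints", but it links these to season and environment in order to justify a short treatment period. A reader might infer that it documents staining variation between Visit 0 and Visit 1; it does not. Slow seasonal change would make the two readings more alike.
- **Visit 0 is not ignored.** Under the baseline definition it is the fallback when Visit 1 is missing. What is absent is its use as a separate term.
- **Changing the ANCOVA alone would be incomplete.** The plan assumes 10% discontinuation, and at 5% or more the primary analysis uses imputation. A covariate in the analysis model but not in the imputation model would be inconsistent. This stands, and the fix allows for it.

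None of this removes the case for the term. It uses data already collected, costs one degree of freedom in about 500 subjects and, in large samples, holds or improves precision.

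**Conclusion.** The point holds as a minor matter of efficiency. The study eye has two staining scores before treatment, and the staining models adjust for one. Adding Visit 0 would reduce tCFS residual variance by about 0% to 13%, taking planned power from 97.9% to about 98–99%, and by a few points more than that if the true difference is nearer -0.7. This rests on assumed correlations, an assumed score distribution for the entry-window simulation, and reading 2.8 as the SD after adjustment for one baseline. No gain has been worked out for cCFS, a single region scored 0–3, or separately for tCFS at Day 15.

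A reader might go further and infer that choosing the eye on a noisy Visit 1 score biases the treatment comparison, inflates the type I error or leaves the trial underpowered. The documents do not support this. Eligibility, eye selection and baseline all come before treatment and apply equally to both randomised arms, so the single-baseline ANCOVA remains valid, and the stated power reproduces for that model.

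**What to change.** Before unmasking:

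1. In SAP 6.5.7.3 and 6.5.8.5 and Protocol 10.4.5 (and the Protocol synopsis, for consistency), add the study eye's Visit 0 score as a second numeric covariate in the staining ANCOVAs: the total score for tCFS, the central score for cCFS. The model statement becomes `MODEL <ENDPOINT>=<TREATMENT> <BASELINE> <VISIT0>`.
2. Keep change defined from Visit 1. Enter Visit 0 as a separate term and do not average the two readings: an average does worse than Visit 1 alone when Visit 0 is the weaker predictor (variance ratio 1.016 at 0.7/0.4/0.5 and 1.067 at 0.6/0.3/0.5).
3. Add the corresponding Visit 0 score to the staining imputation models, by region where staining is imputed by region, and to the repeated-measures sensitivity model in SAP 6.5.7.6.1.
4. State a rule for a missing Visit 0 score, for example to use the Visit 1 value. This should be rare, because the score is an entry criterion. For re-screened subjects, use the Visit 0 that led to randomisation.
5. Leave the Dryness Score model unchanged.

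The cost is a SAP amendment with matching protocol text, small changes to the model and imputation code, and one degree of freedom. No new data are needed.
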